Attachment 2: International Prognostic Scoring System (IPSS) for Myelodysplastic Syndrome

Prognostic Variable	Survival and AML Evolution Score Value				
	0	0.5	1.0	1.5	2.0
Marrow Blasts (%)	<5	5 to 10	n/a	11 to 20	21 to 30
Karyotype ^a	Good	Intermediate	Poor	N/A	N/A
Cytopenias: Neutrophil count <1800/ μ L Platelets <100,000/ μ L Hemoglobin <10 g/dL	0 or 1	2 or 3	N/A	N/A	N/A

a Good: normal or any one of the following: -Y, del 5q, del 20q; Intermediate: any other abnormality; Poor: chromosome 7 abnormalities, complex, ≥ 3 abnormalities
N/A = not applicable.

Risk Category:	Combined Score (Sum of Marrow Blast + Karyotype + Cytopenia Score)
Low	0
Intermediate-1	0.5 to 1.0
Intermediate-2	1.5 to 2.0
High	≥ 2.5

SOURCE: Greenberg P, Cox C, LeBeau MM, et al. International scoring system for evaluating prognosis in myelodysplastic syndromes. Blood 1997;89:2079-2088.

Attachment 3: Eastern Cooperative Oncology Group (ECOG) Performance Status Scale

Grade	Score
0	Fully active, able to carry on all pre-disease performance without restriction
1	Restricted in physically strenuous activity but ambulatory and able to carry out work of a light or sedentary nature, eg, light house work, office work
2	Ambulatory and capable of all self-care but unable to carry out any work activities. Up and about more than 50% of waking hours
3	Capable of only limited self-care, confined to bed or chair more than 50% of waking hours
4	Completely disabled. Cannot carry on any self-care. Totally confined to bed or chair.

SOURCE: Eastern Cooperative Oncology Group (ECOG). http://ecog.dfci.harvard.edu/general/perf_stat.html

Attachment 4: NYHA Classification

The Stages of Heart Failure – New York Heart Association (NYHA) Classification

Class	Subject Symptoms
Class I (Mild)	No limitation of physical activity. Ordinary physical activity does not cause undue fatigue, palpitation, or dyspnea (shortness of breath).
Class II (Mild)	Slight limitation of physical activity. Comfortable at rest, but ordinary physical activity results in fatigue, palpitation, or dyspnea.
Class III (Moderate)	Marked limitation of physical activity. Comfortable at rest, but less than ordinary activity causes fatigue, palpitation, or dyspnea.
Class IV (Severe)	Unable to carry out any physical activity without discomfort. Symptoms of cardiac insufficiency at rest. If any physical activity is undertaken, discomfort is increased.

Heart Failure Society of America The Stages of Heart Failure – NYHA Classification. Available at <http://www.hfsa.org/hfsa-wp/wp/stages-of-heart-failure/>

Attachment 5: Asthma Guidelines

Components of Severity		Classification of Asthma Severity											
		Intermittent			Persistent								
					Mild			Moderate			Severe		
		0-4 yrs	5-11 yrs	12 + yrs	0-4 yrs	5-11 yrs	12 + yrs	0-4 yrs	5-11 yrs	12 + yrs	0-4 yrs	5-11 yrs	12 + yrs
Impairment	Symptoms	≤ 2 days/week			≥ 2 days/week but not daily			Daily			Throughout the day		
	Nighttime awakenings	0	≤ 2x/month		1-2x/month	3-4x/month		3-4x/month	> 1x/week but not nightly		> 1x/month	Often 7x/week	
	SABA use for symptom control (not prevention of EIB)	≤ 2 days/week			≤ 2 days/week but not daily		>2 days/week but not daily, and not more than 1x on	Daily			Several time per day		
	Interference with normal activity	None			Minor limitation			Some limitation			Extremely limited		
	Lung function Normal FEV ₁ /FVC : 8-19 yr 85% 20-39 yr 80% 40-59 yr 75% 60-80 yr 70%	FEV1	N/A	Normal FEV ₁ between exacerbations > 80%	Normal FEV ₁ between exacerbations > 80%	N/A	> 80%	> 80%	N/A	60-80%	60-80%	N/A	< 60%
	FEV1/FVC		> 85%	Normal		> 80%	Normal		75-80%	Reduced		< 75%	Reduced
Risk	Exacerbations requiring oral systemic corticosteroids	0-1/year			≥ 2 exacerbations in 6 months requiring oral steroids or >4 wheezing episodes/1 year lasting >1 day and risk factors for persistent asthma	≥ 2/year Relative annual risk may be related to FEV ₁ .	≥ 2/year Relative annual risk may be related to FEV ₁ .	≥ 2 exacerbations in 6 months requiring oral steroids or >4 wheezing episodes/1 year lasting >1 day and risk factors for persistent asthma	≥ 2/year Relative annual risk may be related to FEV ₁ .	≥ 2/year Relative annual risk may be related to FEV ₁ .	≥ 2 exacerbations in 6 months requiring oral steroids or >4 wheezing episodes/1 year lasting >1 day and risk factors for persistent asthma	≥ 2/year Relative annual risk may be related to FEV ₁ .	≥ 2/year Relative annual risk may be related to FEV ₁ .
Consider severity and interval since last exacerbation. Frequency and severity may fluctuate over time for patients in any severity category.													

Recommended Step for Initiating Treatment	Step 1	Step 2	Step 3 and consider short course of oral steroids	Step 3: medium dose ICS and consider short course of oral steroids	Step 3 and consider short course of oral steroids	Step 3 and consider short course of oral steroids	Step 3: medium dose ICS OR Step 4 and consider short course of oral steroids	Step 4 or 5 and consider short course of oral steroids

* Dysplastic changes should consider the normal range of dysplastic changes (modification).

† Modification to IWG response criteria.

‡ In some circumstances, protocol therapy may require the initiation of further treatment (eg, consolidation, maintenance) before the 4-week period. Such patients can be included in the response category into which they fit at the time the therapy is started. Transient cytopenias during repeated chemotherapy courses should not be considered as interrupting durability of response, as long as they recover to the improved counts of the previous course.

Proposed modified International Working Group response criteria for hematologic improvement

Hematologic Improvement*	Response criteria (responses must last ≥ 8 weeks)†
Erythroid response (pretreatment, < 11 g/dL)	Hb increase by ≥ 1.5 g/dL Relevant reduction of units of RBC transfusions by an absolute number of at least 4 RBC transfusions/8 weeks compared with the pretreatment transfusion number in the previous 8 weeks. Only RBC transfusions given for a Hb of ≤ 9 g/dL pretreatment will count in the RBC transfusion response evaluation†
Platelet response (pretreatment, $< 100 \times 10^9/L$)	Absolute increase of $\geq 30 \times 10^9/L$ for patients starting with $> 20 \times 10^9/L$ platelets Increase from $< 20 \times 10^9/L$ to $> 20 \times 10^9/L$ and by at least 100%†
Neutrophil response (pretreatment, $< 1 \times 10^9/L$)	At least 100% increase and an absolute increase $> 0.5 \times 10^9/L$ †
Progression or relapse after HI‡	At least 1 of the following: At least 50% decrement from maximum response levels in granulocytes or platelets Reduction in Hb by ≥ 1.5 g/dL Transfusion dependence

* Pretreatment counts averages of at least 2 measurements (not influenced by transfusions) ≥ 1 week apart (modification).

† Modification to IWG response criteria.

‡ In the absence of another explanation such as acute infection, repeated courses of chemotherapy (modification), gastrointestinal bleeding, hemolysis, and so forth. It is recommended that 2 kinds of erythroid and platelet responses be reported overall as well as by the individual response pattern.

Notes: Deletions to the IWG response criteria are not shown. To convert hemoglobin levels (concentrations) from grams per deciliter to grams per liter, multiply grams per deciliter by 10.

Abbreviations: CR: complete remission; DFS: disease-free survival; FAB: French-American-British; Hb: hemoglobin; HI: hematologic improvement; IWG: International Working Group; MDS: myelodysplastic syndromes; PFS: progression-free survival; PR: partial remission; RBC: red blood cell

SOURCE: Cheson BD, Greenberg PL, Bennett JM, et al. Clinical application and proposal for modification of the International Working Group (IWG) response criteria in myelodysplasia. Blood 2006;108:419-425.

Attachment 7: Conversion Table for Glucocorticosteroid Dose

Generic Name	Oral or Intravenous Dose (mg)
Dexamethasone	0.75
Hydrocortisone	20
Methylprednisolone	4
Prednisolone	5
Prednisone	5

Attachment 8: The Family of Antihistamine Medications

The following antihistamines may be used for daratumumab preinfusion medication (including, but not limited to):

- Diphenhydramine
- Cetirizine
- Fexofenadine
- Loratadine
- Clemastine
- Dexchlorpheniramine
- Promethazine*

* The IV use of promethazine should be avoided.

Attachment 9: Anticipated Events

Anticipated Event

An anticipated event is an adverse event (serious or non-serious) that commonly occurs as a consequence of the underlying disease or condition under investigation (disease-related) or background regimen.

For the purposes of this study the following events will be considered anticipated events:

Indication related

- Dyspnea
- Fatigue
- Malaise
- Asthenia
- Hemorrhage (with thrombocytopenia)
- Infection
- Cytopenias
 - Thrombocytopenia
 - Neutropenia
 - Febrile neutropenia
 - Leukopenia
 - Lymphopenia
 - Pancytopenia

Population Related

- Arrhythmia, Atrial fibrillation
- Cardiac failure congestive
- Myocardial infarction; Cerebrovascular accident

Reporting of Anticipated Events

All adverse events will be recorded in the eCRF regardless of whether considered to be anticipated events and will be reported to the sponsor as described in Section 12.3.1, All Adverse Events. Any anticipated event that meets serious adverse event criteria will be reported to the sponsor as described in Section 12.3.2, Serious Adverse Events. These anticipated events are exempt from expedited reporting as individual single cases to health authorities. However if based on an aggregate review, it is determined that an anticipated event is possibly related to study drug, the sponsor will report these events in an expedited manner.

Anticipated Event Review Committee (ARC)

An Anticipated Event Review Committee (ARC) will be established to perform reviews of pre-specified anticipated events at an aggregate level. The ARC is a safety committee within the sponsor's organization that is independent of the sponsor's study team. The ARC will meet to aid in the recommendation to the

sponsor's study team as to whether there is a reasonable possibility that an anticipated event is related to the study drug.

Statistical Analysis

Details of statistical analysis of anticipated events, including the frequency of review and threshold to trigger an aggregate analysis of anticipated events will be provided in a separate Anticipated Events Safety Monitoring Plan.

INVESTIGATOR AGREEMENT

JNJ-56022473 (talacotuzumab) and JNJ-54767414 (daratumumab)

Clinical Protocol 56022473MDS2002 – Amendment 4

INVESTIGATOR AGREEMENT

I have read this protocol and agree that it contains all necessary details for carrying out this study. I will conduct the study as outlined herein and will complete the study within the time designated.

1. INTRODUCTION

The purpose of this statistical analysis plan (SAP) is to describe the procedures and the statistical methods that will be used to analyze and report results for study JNJ-56022473-MDS-2002.

2. TRIAL OBJECTIVES

2.1. PRIMARY OBJECTIVE

The primary objective of the study is to evaluate the efficacy (transfusion independence [TI]) of talacotuzumab (JNJ-56022473) or daratumumab in transfusion-dependent subjects with low or intermediate-1 risk MDS whose disease has relapsed during or is refractory to ESAs.

2.2. SECONDARY OBJECTIVES

The secondary objectives of this study are:

- To evaluate the safety of talacotuzumab or daratumumab in the study population.
- To evaluate the clinical benefit of talacotuzumab and daratumumab in this study population through:
 - Time to TI and duration of TI.
 - Rate of HI, CR, and PR.
 - Overall survival (OS).
 - Progression to AML.
 - Rate and amount of supportive care, including transfusions and myeloid growth factors.
- To characterize the PK of talacotuzumab and daratumumab in the study population.
- To evaluate the immunogenicity of talacotuzumab and daratumumab in subjects with MDS.

2.3. EXPLORATORY OBJECTIVES

The tertiary/exploratory objectives of this study are:

- To evaluate pharmacodynamic biomarkers for talacotuzumab activity.
- To determine CD123 and CD38 expression and to explore the association with clinical outcomes.

3. TRIAL DESIGN

3.1. OVERVIEW OF STUDY DESIGN

This is a Phase 2, multicenter, open-label, randomized study to evaluate the safety and efficacy of single-agent talacotuzumab or single-agent daratumumab in subjects with low or intermediate-1 risk MDS who are transfusion-dependent and whose disease has relapsed during or is refractory

to ESA treatment. Approximately 60 subjects (30 to receive talacotuzumab and 30 to receive daratumumab) will be enrolled in this study.

[figure not shown]
The purpose of this study is to separately evaluate 2 agents with different mechanisms of action that may be effective in subjects with low-risk MDS. The design of this study will allow a preliminary assessment of efficacy and safety of both agents, to determine if either or both warrant further evaluation in phase 3 studies. Subjects will be randomized in a 1:1 ratio to receive talacotuzumab or daratumumab. Randomization will be stratified based on number of RBC units transfused burden (4 or >4) during the 8 weeks prior to randomization.

Talacotuzumab will be administered at 9 mg/kg intravenously (IV) every 2 weeks. Daratumumab will be administered at 16 mg/kg IV weekly on Weeks 1 to 8, every 2 weeks for Weeks 9 to 24, and every 4 weeks thereafter. Cycle length is 28 days for both agents. Study drugs will continue to be administered until disease progression, lack of response, unacceptable toxicity, withdrawal of consent, or study end.

The clinical cutoff for the purpose of the primary endpoint analysis will be 6 months after randomization of the last subject. The end of the study is defined as 1 year after the last subject has been randomized or anytime the sponsor terminates the study.

There will be no statistical hypothesis testing, and each arm will be assessed separately. Statistical methods focus on the evaluation of the likelihood that either treatment regimen will result in a true TI rate of 30% or greater against a minimum acceptable value of 15%. A diagram of the study design is provided below in Figure 1.

Figure 1: Schematic Overview of the Study

3.2. STATISTICAL HYPOTHESIS

The primary hypothesis of this study is that the treatment with talacotuzumab or daratumumab separately will produce a TI rate 30% or greater against a minimal acceptable value of 15%. The statistical evaluation of the hypothesis will use a Bayesian approach to assess the likelihood of whether a true TI rate $\leq 15\%$ can be ruled out.

3.3. SAMPLE SIZE JUSTIFICATION

Approximately 60 (30 to receive talacotuzumab and 30 to receive daratumumab) subjects will be enrolled in the study to ensure at least 30 evaluable (see Section 4.3 for definition) subjects in each treatment arm.

On the basis of historical data, the TI rate with treatment of best supportive care is expected to be approximately 7.5% in subjects with low or intermediate-1 risk MDS [17, 22, 23]. The primary objective is to evaluate the likelihood that treatment with talacotuzumab or daratumumab can result in a true TI rate $\geq 30\%$. A true TI rate $\leq 15\%$ (twice the TI rate of best supportive care) will be considered as of no clinical interest in the context of this Phase 2 study. The number of subjects to be randomized into each arm will be 30, which will ensure at least 90% probability that the true TI rate is greater than the minimum acceptable value (MAV) 15% if at least 8 (26.7%) subjects reach transfusion independence. This sample size determination utilizes a Bayesian approach with $Beta(0.5, 0.5)$ as the prior distribution and $Beta(0.5+m, 0.5+30-m)$ as the posterior distribution for the true TI rate, where m is the observed number of subjects who achieve TI.

3.4. STATISTICAL METHODS

The objective of the study is to explore if treatment with talacotuzumab or daratumumab will result in an 8-week RBC TI rate $\geq 30\%$.

There is no statistical hypothesis testing for the primary objective, and there is no formal statistical comparison between the 2 arms. Instead, statistical criteria, based on observed number of subjects achieving TI (number of TIs), are provided to determine if the outcome of each treatment arm is “meeting”, “not meeting” the primary objective, or statistically “inconclusive”. This statistical assessment will be used to guide the decision making for further development of either or both treatment therapies. The evaluation will be performed against the target value (TV) 30% and the minimum acceptable value (MAV) 15% for the TI rate. TV of 30% is defined according to study primary objective and is deemed clinically meaningful. A TI rate below 15%, the MAV, will be of no clinical interest. TI rates between MAV and TV will be considered modest, which will define a statistically inconclusive outcome. The statistical criteria is determined to control false positive and false negative error rates each at 10% level by evaluating its operating characteristics using a Bayesian approach with $Beta(0.5, 0.5)$ as the prior distribution and $Beta(0.5+m, 0.5+N-m)$ as the posterior distribution of the true TI rate, where N is the total number of subjects and m is the observed number of TIs. According to study design, $N=30$ for each treatment arm.

The TI rate point-estimate and the corresponding 2-sided 80% credible intervals (CI) will be calculated for each treatment arm. The 80% CI will be symmetric, i.e., 10% each tail.

Given $N=30$ for each treatment arm, as shown in Figure 2 and Table 1, the lower bound of the 2-sided 80% CI will be $>15\%$ (the MAV) and the upper bound $>30\%$ (the TV) if the observed number of TI is ≥ 8 , meaning statistically 15% TI rate has been ruled out and 30% ruled in, i.e., the study primary objective is “met”. If number of TIs is ≥ 13 , then the outcome will be considered highly desirable as the lower bound of the CI will be $>30\%$ (the TV). Number of TIs ≤ 5 will be an undesirable outcome as the upper bound of the CI is $<30\%$ and the lower bound is $<15\%$, implying the primary objective is “not met”. When number of TI=6 or 7, the outcomes are statistically inconclusive since the lower bound of the CI is $<15\%$ and the upper bound is $>30\%$; and in such a case, results of additional sensitivity analyses and other endpoints (secondary, safety, PK, PD/biomarker) will play a more important role in the decision making.

Table 1: Observed TI, 2-sided Credible Interval, and Statistical Decision Criteria (N=30)

[figure not shown]
| Number (%) of Observed TI | 80% C.I. ¹ | “Meeting” Primary Objective |
|---------------------------|-----------------------|-----------------------------|
| 4 (13.3) | (7.1, 22.9) | No ² |
| 5 (16.7) | (9.6, 26.8) | |
| 6 (20.0) | (12.2, 30.6) | Inconclusive |
| 7 (23.3) | (14.8, 34.3) | |
| 8 (26.7) | (17.6, 37.9) | Yes ³ |
| 9 (30.0) | (20.4, 41.4) | |
| 10 (33.3) | (23.3, 44.9) | |
| 11 (36.7) | (26.2, 48.3) | |
| 12 (40.0) | (29.2, 51.7) | |
| 13 (43.3) | (32.3, 55.0) | |
| 14 (46.7) | (35.4, 58.2) | |

¹ Using $B(0.5, 0.5)$ as the prior distribution for true IT rate

² With false negative error rate $<10\%$; i.e., when observing # of TI ≤ 5 , there is a $<10\%$ chance that the true TI rate is $\geq 30\%$

³ With false positive error rate $<10\%$; i.e., when observing # of TI ≥ 8 , there is a $<10\%$ chance that the true TI rate is $\leq 15\%$

Figure 2: Plot Showing the Decision Rule for Each Treatment Arm

The statistical method described in this section is also applicable if the number of subjects in each arm is not 30, in which case the posterior distribution corresponding to the actual sample size will be used.

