6.1.3. ANALYSIS METHODS

Number and percent of subjects achieving TI and the corresponding 2-sided 80% confidence

interval (CI) will be summarized.

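### SAP 3.4 says 8 or more responders of 30 rules in a 30% TI rate, but the rule only leaves 30% not excluded; at 8/30 the plan's own posterior gives P(rate ≥ 30%) = 35.4%

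*SAP*

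**What the plan says.** SAP 3.3 frames the aim around the 30% target: "The primary objective is to evaluate the likelihood that treatment with talacotuzumab or daratumumab can result in a true TI rate" of 30% or more. SAP 3.4 sets a target value (TV) of 30% and a minimum acceptable value (MAV) of 15%. It uses a Beta(0.5, 0.5) prior and an 80% equal-tailed credible interval, and classifies results at N = 30 as follows.

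- **8 or more TIs:** lower bound above 15% and upper bound above 30%, "meaning statistically 15% TI rate has been ruled out and 30% ruled in"; objective met.
- **6 or 7:** "When number of TI=6 or 7, the outcomes are statistically inconclusive since the lower bound of the CI is" below 15% and the upper bound is above 30%.
- **5 or fewer:** upper bound below 30%; not met.
- **13 or more:** "then the outcome will be considered highly desirable as the lower bound of the CI will be" above 30%.

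On other sample sizes it adds: "The statistical method described in this section is also applicable if the number of subjects in each arm is not 30". Earlier in the section it says: "TI rates between MAV and TV will be considered modest, which will define a statistically inconclusive outcome". Protocol 11.3 has that last sentence and the same cutoffs, but it rests the 8-responder threshold on the lower bound alone and never says that 30% is ruled in.

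On reporting, SAP 3.4 states: "The TI rate point-estimate and the corresponding 2-sided 80% credible intervals (CI) will be calculated for each treatment arm". SAP 6.1.3 instead plans: "Number and percent of subjects achieving TI and the corresponding 2-sided 80% confidence" interval.

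**The concern.** An upper bound above a value shows that the value is still plausible; it does not show that the rate reaches it. The SAP uses that bound to claim 30% at 8 responders, while the same condition at 6 and 7 leaves the result inconclusive. Only the lower bound separates 8 from 7, and it speaks to 15%, not 30%.

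This matters because the objective is expressed as a rate of at least 30% and the assessment is meant to guide further development. A met result with a lower bound below 30% could be reported as having established the target.

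Two related inconsistencies feed the same misreading. The sentence tying rates between MAV and TV to an inconclusive outcome does not match Table 1. And the probability that SAP 3.3 names as the objective, P(rate ≥ 30%), is not listed as an output in SAP 3.4 or 6.1.3.

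**Working it through.** **Inputs (SAP 3.4):** N = 30; prior Beta(0.5, 0.5); posterior Beta(0.5 + m, 0.5 + 30 − m) for m responders; 80% interval from the 10th and 90th posterior percentiles; MAV 15%; TV 30%.

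**1. Reproduce the plan.** All 11 rows of SAP Table 1 (m = 4 to 14) reproduce. For m = 8 the posterior is Beta(8.5, 22.5), with 10th and 90th percentiles 17.58% and 37.91%; Table 1 prints 17.6 and 37.9. Both error footnotes hold at their limiting counts: P(rate ≤ 15% | 8/30) = 4.5% and P(rate ≥ 30% | 5/30) = 4.9%, each below 10%.

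**2. What each bound means.** With 10% in each tail:

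- lower bound > 15% is equivalent to P(rate > 15%) > 90%;
- upper bound > 30% is equivalent to P(rate ≥ 30%) > 10%;
- lower bound > 30% is equivalent to P(rate > 30%) > 90%.

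The first and third are demonstrations. The second is only a failure to exclude.

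**3. Posterior probabilities at N = 30.**

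| TIs | 80% interval (%) | P(rate > 15%) | P(rate ≥ 30%) | SAP label |
|---|---|---|---|---|
| 6 | 12.2 to 30.6 | 78.6% | 11.3% | Inconclusive |
| 7 | 14.8 to 34.3 | 89.5% | 21.6% | Inconclusive |
| 8 | 17.6 to 37.9 | 95.5% | 35.4% | Met |
| 9 | 20.4 to 41.4 | 98.3% | 51.1% | Met |
| 10 | 23.3 to 44.9 | 99.5% | 66.3% | Met |
| 11 | 26.2 to 48.3 | 99.8% | 79.0% | Met |
| 12 | 29.2 to 51.7 | >99.9% | 88.2% | Met |
| 13 | 32.3 to 55.0 | >99.9% | 94.1% | Met, highly desirable |

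At 8/30 the rate is more likely below 30% (100% − 35.4% = 64.6%) than at or above it. P(rate ≥ 30%) first passes 90% at 13. The prior does not drive this: at 8/30 the figure is 38.6% under Beta(1, 1) and 32.1% under a prior close to Beta(0, 0).

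**4. How often the unsupported claim would arise.** X ~ Binomial(30, p); P(8 ≤ X ≤ 12) is 7.0%, 23.6% and 46.4% at assumed true rates p of 15%, 20% and 25%. P(X ≥ 8) is 7.0%, 23.9% and 48.6%, so almost every met result at these rates would fall in 8 to 12.

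**5. Other sample sizes.** The documents give no final N, so these values are assumed.

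| N | First met count | P(rate ≥ 30%) there | First count with lower bound > 30% |
|---|---|---|---|
| 28 | 7 | 28.9% | 12 |
| 29 | 7 | 25.0% | 12 |
| 30 | 8 | 35.4% | 13 |
| 31 | 8 | 31.3% | 13 |
| 32 | 8 | 27.4% | 13 |
| 33 | 8 | 23.9% | 14 |

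**6. The sentence on rates between MAV and TV.** Read as observed rates, the counts strictly between 15% and 30% are 5, 6, 7 and 8 of 30 (16.7%, 20.0%, 23.3%, 26.7%). Table 1 labels them No, Inconclusive, Inconclusive and Yes. Read as true rates, 60.1% of the posterior at 8/30 lies between 15% and 30%, yet 8/30 is met. Neither reading fits the table.

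**7. The interval label.** At 8/30 an 80% Clopper-Pearson confidence interval is 16.2% to 39.7%, against the credible 17.6% to 37.9%. The printed interval therefore depends on the word used. No N = 30 boundary moves: the Clopper-Pearson bounds are 28.7% (upper, 5/30), 32.5% (upper, 6/30), 13.5% (lower, 7/30), 16.2% (lower, 8/30), 27.7% (lower, 12/30) and 30.8% (lower, 13/30).

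**The case against.** The best defence is that this is loose wording which its surroundings already limit. The same sentence states the two bounds, the next reserves a lower bound above 30% for 13 or more, and the footnote to Yes concerns only rates of 15% or less. The hypothesis sections (protocol 2.2, SAP 3.2) say the evaluation asks whether 15% can be excluded. The interval will be reported, so a lower bound below 30% would be visible. The inconclusive rule is explicit despite the introductory sentence on intermediate rates. The label conflict is a separate slip.

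Much of this stands. It shows that the cutoffs and classifications are sound. The 23.6% and 46.4% are chances of landing on 8 to 12 at chosen true rates, not rates of misreporting. The 35.4% is the value at the threshold; it rises to 88.2% at 12. The posterior share in step 6 is not a criterion the plan adopts.

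It does not rescue the phrase. The surrounding text contradicts the claim that 30% is ruled in, and because the objective is stated as a rate of at least 30%, a reader who sees it called met has reason to take the phrase literally.

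**Conclusion.** The concern holds. A met result shows that the rate exceeds 15%; it does not establish 30% unless the lower bound exceeds 30%, which at N = 30 needs 13 responders. For 8 to 12 responders, P(rate ≥ 30%) runs from 35.4% to 88.2%, short of the 90% that the SAP's interval requires. These figures rest only on the SAP's prior, N = 30 and its 80% equal-tailed interval; the frequencies in step 4 and the grid in step 5 rest on assumed true rates and sample sizes. No classification changes, only what a met result may claim. It should be fixed before results are written up.

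A minor, separate conflict concerns the rationale for the 15% floor. Protocol 11.2 calls it 6 times a supportive-care rate of 2.5%; SAP 3.3 calls it twice a rate of 7.5%. The protocol cites its reference 17 for the 2.5%, but item 17 in its list is a paper on daratumumab in multiple myeloma. The documents do not settle which rate is right, and neither enters the posterior.

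**What to change.** - **SAP 3.4, the met sentence:** say that 30% is not ruled out. Add: *For the N analysed, met means that the 80% lower bound exceeds 15% and the upper bound exceeds 30%. The TV is established only if the lower bound exceeds 30% (at N = 30: met from 8, TV established from 13).*
- **SAP 3.4, and protocol 11.3 if next amended, the sentence on intermediate rates:** *True TI rates from MAV to TV are regarded as modest. A result is inconclusive when the 80% lower bound is not above 15% and the upper bound is not below 30%.*
- **SAP 6.1.3:** change confidence to credible, and report P(rate > 15%) and P(rate ≥ 30%) from the SAP 3.4 posterior at the actual N.
- **Minor:** reconcile the supportive-care rate and its citation between protocol 11.2 and SAP 3.3, and restate the multiple that 15% represents.

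Keep the cutoffs, the 15% floor and N. The cost is a few sentences, one changed word, two extra outputs from a posterior already specified, and one citation check; no new data are needed. The one drawback for the sponsor is that a met result with a lower bound below 30% will read less favourably.
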